Genome-wide gene expression analysis of prostate carcinomas will compare expression profiles among groups (e.g., African-American versus Caucasian, high versus low IGF-1) that consist of 10-30 tumors per group. The minimum number of tumors needed to generate a molecular profile that differentiates two groups cannot be determined for the proposed experiments. A best estimate is 13 per group based on the following assumptions: A significance level of 0.001 and a power of 0.05, assuming the data is base 2log transformed and that the variance in expression for a gene of interest is 0.5, and that one wishes to be able to detect genes for which one of the four subgroups exhibits a two-fold change in expression at the specified power (using the nQuery software). However, some recent PCa gene expression studies used fewer tissues than we are proposing for our experiments and yielded expression signatures that predicted clinical behavior in response to treatment (84,85) or differentiated tumors according to

NCI IRB Approval:	October 28, 2004
Protocol Number:	05-C-N021

the Gleason score (93). Thus, the proposed sample size for our investigations appears be adequate and is still suitable to do laser-captured microdissection. [name] at the Advanced Computing Center at the NCI-Frederick will conduct the analysis of the expression data.

Target Accrual Numbers of Cases and Controls ¹			
	African-American	Caucasian Males	Total
	Males		
Cases	500	500	1000
Population	500	500	1000
Controls			
Total	1000	1000	2000
¹ Race will be identified by subject self-report			

 Table 7: Target Accrual Numbers for the Proposed Study (as of 2010)

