5.4.2 AVAILABILITY OF CASES AND JUSTIFICATION OF SAMPLE SIZE

A review of cancer registry data shows that the 2 participating hospitals treated 313 PCa cases in 2001 of which 150 cases were identified as being of African-American and 143 cases as being of Caucasian descent (Table 8). Twenty cases were either not informative for race or had a different race/ethnic background (e.g., Asian, Hispanic). Most of the cases had residency in the greater Baltimore area. There were 52 known available cases with radical prostatectomy in 2001, which is sufficient to meet our goal of recruiting at least 25 cases with radical prostatectomy per year.

We will use the case-control design to detect statistically significant differences in the frequency of genotypes between PCa patients and randomly selected population-based controls that are matched by age, gender and race to the cases. For the initial analysis, all cases will be grouped together. We will then examine the study population stratified by race and/or exposure. The study is designed to detect risk associations that have odds ratios of ≥ 1.5 . Associations between PCa and genotypes of the angiogenesis and hormone pathways have been found to have odds ratios that are in the range of 1.5-2.5 (39,69-71). Examples are shown in Table 3. We are not aiming to detect weak risk associations that are reflected by odd ratios between 1 and 1.5. Such associations are prone to a selection bias and confounding, and would require a larger sample. Our proposed study is exploratory and designed to detect potentially novel genotype–cancer risk associations. The finding of a new disease-associated genotype can subsequently be validated in a larger study.

Known Available Cases by Hospital Calendar Year 2001					
	African-American Caucasian Total				
VA Hospital	85	48	133		
All Cases					
UM Medical Center	65	95	160^{-1}		
All Cases					
Total	150	143	293		
1 >70% of patients are from the greater Baltimore area					

Table 8: Known Available Cases from Hospital Tumor Registries

POWER CALCULATIONS

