wild-type genotype (major allele), or the lowest exposure subgroup, as the reference group. Odds ratios and 95% confidence intervals will be calculated by unconditional logistic regression. Regression analysis will be performed in univariate and multivariate models to assess associations between risk factors and cancer susceptibility, and to adjust for possible confounding factors. Case-case analyses, correlating tissue marker expression with tumor staging, hormone blood concentrations, diet or genotypes, will be done by ANOVA, with the student's t-test, or a nonparametric test, such as the Mann-Whitney U rank sum test. To look at trends, the Mantel-Haenszel test for trend will be used to assess the correlation between marker expression/frequency and categorized (e.g., low, medium, high) variables, such as tumor stage, intake of a dietary factor, or IGF-1 blood concentrations. The association between a genotype and outcome will be studied either in a logistic regression model after categorizing into a good and poor outcome group or with the Kaplan-Meier method and the log-rank test. All analyses will be performed with the STATA and SAS statistical software packages.

ANALYSIS OF GENE EXPRESSION PROFILES

The data from the Affymetrix HG-U133A array will be estimated using the RMA procedure from Bioconductor (www.bioconductor.org). Previous analysis on raw data from replicate samples with RMA indicates that the mean standard deviation of log2 intensities is 0.1 across all intensity levels. This corresponds to a typical technical error of 5%-10% (94).

The factorial study design suggests an analysis of variance. We will first examine the four groups for heterogeneity of variances by comparing the ratios of variances between groups to the F-distribution. If the distributions conform, we will follow standard ANOVA procedure. If there is significant departure from agreement, we will perform non-parametric ANOVA using the rank F-test and use the Welch t-test for two group comparisons. We will select differentially expressed genes for contrasts between racial groups at each level of tumor, and for the difference between tumor stages across racial groups. To address the multiple comparisons problem we will use a modified FDR procedure of Benjamini and Hochberg adapted to correlated data (95).

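### The expression plan answers unequal variances with a rank F-test that is not valid under them, and its variance pretest sends some heteroscedastic genes to pooled-variance contrasts, inflating the high-stage race list and the stage list when high-stage tumors vary more

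*Protocol*

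**What the plan says.** Protocol section 5.4.3, under the analysis of gene expression profiles, sets a two-step rule for a four-group (race by stage) design.

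- **Pretest:** "We will first examine the four groups for heterogeneity of variances by comparing the ratios of variances between groups to the F-distribution".
- **If variances agree:** the standard ANOVA procedure.
- **If they do not:** "If there is significant departure from agreement, we will perform non-parametric ANOVA using the rank F-test". The same sentence goes on: "and use the Welch t-test for two group comparisons".
- **Gene selection** (by contrasts between and across the two races): "We will select differentially expressed genes for contrasts between racial groups at each level of tumor, and for the difference between tumor stages across racial".
- **Multiplicity:** "we will use a modified FDR procedure of Benjamini and Hochberg adapted to correlated data". No FDR level is given.

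Table 6 (section 1.2.4) plans 20-30 low-stage (pT2) and 10-20 high-stage (pT3) tumors in each race. The imbalance is therefore between stages, not between races.

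**The concern.** The rank F-test assumes that, under the null, all groups share one distribution, including its spread. Ranks inherit unequal spread, so the test named for unequal variances does not hold its level under them, least of all when group sizes differ.

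The other branch has its own weakness. A gene whose variances truly differ, but which the pretest fails to flag, gets contrasts built on one error variance pooled over all four groups. When the small groups are the more variable, that pooled variance is too small for any contrast that leans on them.

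An FDR procedure controls errors only if the p-values fed into it are valid. Race differences in same-stage tumors, including high-stage tumors, are the first secondary objective in section 1.1.

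**Working it through.** **Inputs.** Group sizes come from Table 6, taken as low/high/low/high for the two races: 20/10/20/10, 30/10/30/10 and 30/20/30/20. The nominal level 0.001 is the per-gene significance level in the sample-size text of section 5.4.1; 0.05 is shown for comparison. Assumptions: normal data, equal means, high-stage SD 1.5 or 2 times low-stage SD, and the pretest run gene by gene as six pairwise variance-ratio tests at 0.05 (the protocol gives no level). Only the SD ratio matters under the null, so the variance assumed for the sample size is not needed. The protocol states no error rate for these tests, so there is no figure of its own to reproduce.

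**Step 1. Rank F-test, rejection of null genes by simulation.**

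| Sizes | SD ratio | at 0.05 | at 0.001 |
|---|---|---|---|
| 20/10/20/10 | 1.5 | 0.073 | 0.0031 |
| 20/10/20/10 | 2 | 0.092 | 0.0047 |
| 30/10/30/10 | 1.5 | 0.081 | 0.0028 |
| 30/10/30/10 | 2 | 0.110 | 0.0062 |
| 30/20/30/20 | 1.5 | 0.064 | 0.0018 |
| 30/20/30/20 | 2 | 0.077 | 0.0031 |

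If instead the larger low-stage groups have twice the SD, the test is conservative at 0.05 (0.026 to 0.044). With SD ratios 1.5 to 3, Welch ANOVA rejects 0.051 to 0.054, and two-group Welch t-tests 0.047 to 0.052.

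**Step 2. Why pooled contrasts go wrong.** Set the low-stage variance to 1 and the high-stage variance to 1.5² = 2.25. The expected pooled variance is Σ(nᵢ−1)σᵢ²/(N−4).

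- 30/10/30/10: (58×1 + 18×2.25)/76 = 98.5/76 = 1.296
- 20/10/20/10: (38×1 + 18×2.25)/56 = 78.5/56 = 1.402
- 30/20/30/20: (58×1 + 38×2.25)/96 = 143.5/96 = 1.495

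True variance of a contrast divided by the variance the pooled analysis assumes, before conditioning on the pretest:

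- Race within high stage: 2.25/1.296 = 1.74; 2.25/1.402 = 1.60; 2.25/1.495 = 1.51.
- Stage averaged over races, (1/n_low + 2.25/n_high) / [pooled × (1/n_low + 1/n_high)]: 0.2583/0.1728 = 1.50; 0.275/0.2103 = 1.31; 0.1458/0.1246 = 1.17.
- Race within low stage: 1/1.296 = 0.77; 1/1.402 = 0.71; 1/1.495 = 0.67, which is conservative.

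**Step 3. The full two-step rule.** 200,000 simulated null genes; pooled contrast if the pretest passes, Welch-type contrast if it fails. This is the reading of the fallback most favorable to the plan. Nominal 0.001, SD ratio 1.5:

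| Sizes | Genes passing | Race, high stage (Welch throughout) | Stage (Welch throughout) |
|---|---|---|---|
| 30/10/30/10 | 30% | 0.0043 (0.0008) | 0.0027 (0.0009) |
| 20/10/20/10 | 36% | 0.0039 (0.0008) | 0.0021 (0.0010) |
| 30/20/30/20 | - | 0.0021 (0.0009) | 0.0012 |

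The simulation error at 0.004 is √(0.004×0.996/200,000) ≈ 0.00014. Race within low stage stays at 0.0008 to 0.0009.

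At SD ratio 2 fewer genes slip through. Race within high stage is about 0.0025 with 10 high-stage tumors per race and 0.0011 with 20; stage is about 0.0019 and 0.0010. A stricter pretest makes matters worse: with Bonferroni-corrected pairwise tests, race within high stage rises to 0.0078 (30/10/30/10, ratio 1.5).

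**Step 4. Reverse direction.** If low-stage tumors are the more variable, race within low stage rises slightly, to about 0.0015-0.0017.

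**The case against.** The strongest reply is that the fallback sentence does not end with the rank F-test. It assigns the Welch t-test to two-group comparisons, and the gene lists are chosen by contrasts. Race at a given stage is a two-group comparison, and the rank F-test may be only an omnibus step that selects nothing. This stands, and it limits the harm from the rank F-test to two cases: the omnibus test itself selects genes, or the stage difference across races means a race-by-stage interaction tested on ranks. In the second case rejection at nominal 0.05 is 0.060 to 0.116 for SD ratios 1.5 to 3. The text settles neither. A reader might infer from the rank F-test alone that every race and stage list is contaminated, or turn its omnibus rates into a count of false genes per list; the protocol supports neither step. The reply does not reach Step 3, where Welch was already granted in the fallback.

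Three further points are fair. No section says that high-stage tumors are the more variable. The classical F-test is worse than the rank F-test in the liberal cases, so the switch does reduce the error. And at nominal 0.05 with SD ratio 2, the two-step contrasts reject 0.048 to 0.054; the excess there lies in the far tail, which is where gene selection operates.

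A reader might also see hospital confounding, since the model names only race and stage, and Table 8 ("Known Available Cases by Hospital Calendar Year 2001") shows 85 of 150 African-American but 48 of 143 Caucasian cases at the VA hospital. The documents do not support that as a finding. The table counts all treated cases, not the prostatectomy patients who supply tumors. No hospital effect on expression is shown. Section 3.1.2 routes resected tumors to one pathology department. Model covariates are also commonly left to an analysis plan.

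**Conclusion.** The point holds in a limited form. The rank F-test is the wrong remedy for unequal variances with Table 6's stage groups: about 0.065 to 0.11 at nominal 0.05 if the high-stage SD is 1.5 to 2 times the low-stage SD, and conservative in the reverse case. Even with Welch in the fallback, the pretest rule at nominal 0.001 and SD ratio 1.5 rejects about four times too often for race within high stage, and two to three times too often for stage, with 10 high-stage tumors per race. With 20 per race the excess is about twofold for race within high stage and negligible for stage.

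These sizes rest on the assumed SD ratios, normal data and the assumed pretest level. The conclusion covers the high-stage race list and the stage list when high-stage tumors are the more variable. It does not cover every list or every direction.

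**What to change.** In section 5.4.3:

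- Remove the variance pretest and the rank F-test.
- For every gene, test race within each stage and stage across races with Welch-type contrasts (group-specific variances, Satterthwaite degrees of freedom).
- If an omnibus test is kept, use Welch ANOVA. It still runs slightly above nominal in the tail (0.0011 to 0.0020 at 0.001), so the contrasts should drive selection.
- Say whether the stage comparison across races is an average stage effect or a race-by-stage interaction. A Welch-Satterthwaite contrast serves either; for the interaction it rejects 0.047 to 0.051 at nominal 0.05.
- State which test produces each gene list, then apply the planned FDR procedure.

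The cost is analysis code, and slightly less power for genes whose variances are truly equal. No tumors or data are added.

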The reasons for the large racial and geographic differences are poorly understood but both environmental and genetic risk factors are thought to be involved. Migrant studies support the involvement of environmental factors (2-4). The adoption of a Western-type diet has been found to strongly increase the risk for PCa (5,6). High meat and animal fat intake, and excessive alcohol consumption, correlate positively with PCa risk (7-9), while a diet that is either high in phytoestrogens (10), such as a soy diet, or in allium vegetables (11) appears to be protective. Although smoking does not appear to be associated with the incidence of PCa (12,13), an association between current smoking and high grade or metastatic PCa has been reported (14-17). It suggests that smoking promotes the progression to a more advanced disease. Other observations point to the role of genetic susceptibility factors in human PCa. The lifetime risk of PCa increases 1.5 to 4-fold in men with one or two first-degree relatives with PCa (18). A Scandinavian study of twins estimated that 42% (95% CI: 29% - 50%) of the observed PCa susceptibility was associated with inherited genetic risk factors (19). Genetic risk factors are particularly significant at a younger age, and the attributable risk of inherited susceptibility is thought to be as high as 30%-40% among men diagnosed with PCa at age 55 years or younger (18). The importance of genetic susceptibility is further suggested by the finding that only humans and dogs, but not other mammals develop PCa (20). Recent reports indicate that PCa biology is different in African-Americans when compared with Caucasians. African-American men develop higher stage carcinomas earlier in life than Caucasian men (21). It appears that both an earlier onset and a more rapid progression of the disease in African-Americans contribute to the difference in mortality between the two ethnic groups (22). Such observations are supported by additional data. The Prostate Cancer Outcomes Study concluded that traditional socioeconomic, clinical, and pathologic factors, could not explain the increased risk of advanced-stage PCa in African-American men (23). Autopsy examination of prostate specimens revealed that the frequency of small latent carcinomas is similar in low-risk and high-risk populations (4,24). In contrast, larger and highergrade carcinomas are more common in high-risk than in low-risk populations, and the frequency correlates with the incidence of clinical PCa. The data show that genetic and/or environmental factors modulate the progression from a small, microscopic carcinoma into a large carcinoma (4,25), and that tumor progression is the critical step that defines the strong ethnic differences in PCa risk and mortality.

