1.1 STUDY OBJECTIVES

PRIMARY OBJECTIVE

We will examine the association of allele variant genes with PCa risk. The key aim is to examine pathways in relation to PCa, e.g., host defense, inflammation pathways. Within cases, we will examine the relation of genetic variants to molecular, clinical, and prognostic endpoints. The objective will be accomplished with 1) genotype analysis of blood DNA from 1000 cases and 1000 controls and 2) collection of data from questionnaires, medical and pathology records, and the National Death Index. We are testing the hypothesis that susceptibility to nonhereditary PCa is modified by allele variant genes that modulate host defense, inflammation, hormone-stimulated survival and proliferation of mutant cells, the DNA repair capacity, or tumor angiogenesis. The susceptibility may vary by race and lifestyle (gene-environment interaction).

SECONDARY OBJECTIVES

- We will develop gene expression profiles of 60-100 tumors, and will compare gene expression in low-stage and high-stage tumors of African-Americans with gene expression in same stage tumors of Caucasians. The objective is to find gene expression profiles of cancerous and non-cancerous prostate tissue that are characteristic for the disease in African-American men. *We are testing the hypothesis that the molecular signature of primary prostate tumors is different between African-American and Caucasian men. The gene expression profile of African-Americans is associated with an early onset of the disease, a more rapid cancer progression and poor outcome.*
- We will examine the gene expression profiles of tumors from current (n = 10-15) and never smokers (n =10-15). We are testing the hypothesis that current smoking induces a gene signature of tumor progression that reveals the mechanism by which tobacco smoke promotes prostate cancer progression.
- We will determine IGF-1 serum concentrations in our study population and compare gene expression profiles of about 10-15 low-stage tumors from patients with blood IGF-1 levels in the extreme quartiles, respectively. We are testing the hypothesis that a high IGF-1 blood concentration modulates gene expression in primary tumors. The molecular profile is associated with disease progression and poor outcome.

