Recent progress in whole genome expression profiling has generated prognosisrelated molecular profiles for many cancer types (81-83). A four-gene expression model has been described that discriminated between seven PCa patients with relapse and seven PCa patients without relapse, independently of stage and grade (84). The gene expression profiles were obtained from clinically localized tumors that were removed by radical prostatectomy. Another research group studied a group of 23 PCa patients, who were treated with adjuvant androgen suppression therapy before surgery (85). The surgical specimens were investigated for correlations between a patient's gene expression profile and disease recurrence with a 5-year follow-up. An eight-gene signature was identified that classified patients into a PCa recurrence group and a non-recurrence group with an overall correct prediction of 83%. A combination of gene profile and clinical/pathological parameters yielded a correct prediction of 96%.

Although these investigations have shown that gene expression profiles can predict PCa recurrence, there is no such study in the literature that has attempted to identify the genes and pathways with relevance to the etiology and aggressive behavior of PCa in African-Americans. Our objective is to find molecular signatures of low-stage and high-stage tumors in African-Americans, and to identify genes that are relevant to metastasis and patient outcome. The research is also aimed at determining molecular profiles in the context of lifestyle and diet if a strong association between a lifestyle/dietary component and cancer risk has been reported or can be established in our study population. We expect to collect up to 100 fresh-frozen tumor specimens that 1) are primarily identified by PSA screening, 2) are positive for cancer by needle biopsy, and 3) are surgically removed by radical prostatectomy. Of those, we expect that about 25% of the patients will have an advanced pathological stage (\geq pT3) or a Gleason score \geq 7 (86). Of the 52 patients, who underwent radical prostatectomy at the 2 participating hospitals in 2001, 49 were informative for staging and 24.5% of these had an advanced pathological stage (Table 5).

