We will investigate gene expression patterns in both tumor tissue and the surrounding non-tumor tissue. We will develop gene expression profiles of 60-100 microdissected tumors (Table 6). We hypothesize that gene products of both tumor and stromal cells drive tumor progression and the invasion of normal surrounding tissue. We will use laser-captured microdissection to separate tumor from normal tissue, and to determine the molecular profiles that separate 1) PCa in African-Americans from PCa in Caucasians, 2) high pathological stage from low pathological stage tumors, and 3) poor

NCI IRB Approval:	October 28, 2004
Protocol Number:	05-C-N021

from good outcome. Candidate marker genes for tumor progression and outcome will be validated by quantitative PCR, and will be further studied.

 Table 5: Stage Distribution of 49 PCa Patients Undergoing Radical Prostatectomy at the Two Participating Hospitals

Calendar Year 2001	
Pathological Stage	Number of Patients
Stage I + II	37
Stage III	11
Stage IV	1

Table 6: Tumors for Expression Profiling Stratified by Race and Pathological Stage

Race	Pathological stage	Number of specimens
African-American	Low (pT2)	20-30
	High (pT3)	10-20
Caucasian	Low (pT2)	20-30
	High (pT3)	10-20

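### The expression ANOVA compares races within pT stage with no Gleason term, so a grade imbalance between races could not be told apart from a race signature

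*Protocol*

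**What the plan says.** The first secondary objective (Protocol 1.1) is to "compare gene expression in low-stage and high-stage tumors of African-Americans with gene expression in same stage tumors of Caucasians". Table 6 in 1.2.4, headed "Tumors for Expression Profiling Stratified by Race and Pathological Stage", plans 20-30 pT2 and 10-20 pT3 tumors for each race.

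Section 5.4.3 (analysis of gene expression profiles) turns this into a four-group ANOVA. On gene selection it says: "We will select differentially expressed genes for contrasts between racial groups at each level of tumor". A second set of contrasts compares stages across races. Multiplicity is handled by a false discovery rate (FDR) procedure. Grade is not mentioned. The confounder adjustment earlier in 5.4.3 belongs to the case-control logistic regression, not to this ANOVA.

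Gleason does appear elsewhere:

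- **5.4.3, analysis of genotypes:** cases may be split by pT stage or, alternatively, by Gleason score (6 or lower versus 7 or higher).
- **5.4.1:** an earlier expression study is cited because its profiles separated tumors by Gleason score.
- **1.2.4:** about a quarter of the specimens are expected to be at least pT3 or to have Gleason 7 or higher. The hospital figure given in support is "49 were informative for staging and 24.5% of these had an advanced pathological stage".

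On how grade varies between populations, the Introduction says that larger and higher-grade "carcinomas are more common in high-risk than in low-risk populations". The Introduction and 1.2.2 place African-American men at the highest incidence.

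**The concern.** The hypothesis in 1.1 is that the molecular signature of primary tumors differs between African-American and Caucasian men. Restricting the comparison to tumors of the same pT stage removes stage as an explanation but leaves grade free to differ.

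Both links that make grade an alternative explanation come from the protocol itself. Expression varies with Gleason (5.4.1), and grade varies with population risk (Introduction). The FDR procedure limits chance findings. It does nothing about a systematic shift. The monitoring list in 5.6 names the stage distribution of frozen specimens but not their grade, so an imbalance could also pass unnoticed during accrual.

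What is at stake is interpretation. A list of genes that differ by race within pT2 could reflect race-related biology at a given grade, a different grade mix, or both, and the stated analysis gives no means of separating them.

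**Working it through.** **1. The plan's own figure.** Table 5 gives 37 patients in stage I+II, 11 in stage III and 1 in stage IV, total 49. Then (11 + 1)/49 = 12/49 = 24.5%, which reproduces. The count uses pathological stage alone. In the same patients the share with advanced stage or Gleason 7+ cannot be smaller than the share with advanced stage, so 24.5% is a lower bound for the stage-or-Gleason share. The protocol gives no count for the latter.

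**2. Bias in the race contrast.** Let p1 and p0 be the Gleason 7+ shares of the two races within a pT cell, and b the grade effect on a gene in log2 units. With no true race effect, the expected race difference is b × (p1 − p0). It is zero when the shares are equal.

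**3. Inputs.**

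| Input | Value | Source |
|---|---|---|
| b | 1 log2 unit | assumed; the two-fold change used for sizing in 5.4.1 |
| Within-grade SD | 0.5 and 0.71 | assumed; 5.4.1 prints variance 0.5, SD √0.5 = 0.71; 0.5 covers a reading of that figure as an SD |
| n per race, pT2 | 20 and 30 | Table 6 |
| Shares p1, p0 | 50% v 30%; 70% v 30% | assumed; none in the protocol |

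The biases are 1 × 0.20 = 0.20 and 1 × 0.40 = 0.40 log2.

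**4. Standard error.** A grade mixture also adds variance within each race:

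SE = √{[2·SD² + b²·p1(1 − p1) + b²·p0(1 − p0)]/n}

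For SD 0.5, n = 30, 50% v 30%: √{(0.50 + 0.25 + 0.21)/30} = √0.032 = 0.179, so the shift is 0.20/0.179 = 1.12 standard errors.

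For SD 0.5, n = 30, 70% v 30%: √{(0.50 + 0.21 + 0.21)/30} = 0.175, so the shift is 0.40/0.175 = 2.28 standard errors.

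**5. Rejection rates.** Simulated two-sample t-tests, 40,000 runs per row, no true race effect:

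| SD | n | 50% v 30%: at 0.05 | at 0.001 | 70% v 30%: at 0.05 | at 0.001 |
|---|---|---|---|---|---|
| 0.71 | 20 | 11% | 0.6% | 32% | 3.3% |
| 0.71 | 30 | 15% | 0.8% | 44% | 6.8% |
| 0.5 | 20 | 15% | 0.9% | 44% | 6.9% |
| 0.5 | 30 | 20% | 1.5% | 61% | 14% |

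Allowing for simulation error between runs, the ranges are about 11-20% and 31-61% at 0.05, and about 0.5-1.6% and 3-14% at 0.001. With 30% in both races the rates stay near 5% and 0.1%. At the smallest pT3 cell (n = 10) the inflation is less: about 8-10% and 18-25% at 0.05.

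**6. Check on the SD reading.** Dividing the bias by SD·√(2/n) alone gives up to 34% and 87% at 0.05, reached at SD 0.5 and n = 30. That treats 0.5 as the total SD. A 1 log2 grade effect at a 50% share contributes variance 0.25 by itself, which is all of 0.5², leaving no within-grade variation. Those higher figures should not be used. If instead the printed variance of 0.5 is the total, the within-grade variance at shares of 30-50% is 0.25-0.29 (SD 0.50-0.54), which is close to the SD 0.5 rows.

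**The case against.** Much of the opposing case stands.

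- **No contradictory definition.** A reader might infer that 1.2.4 defines advanced disease as a stage-or-Gleason composite while Table 6 and 5.4.3 use stage alone. The text does not support that. Section 1.2.4 forecasts the specimen mix. There "advanced" qualifies pathological stage, and Gleason is a separate feature joined by "or". The objective, Table 6 and the ANOVA all use pT stage consistently. Harmonizing the wording would change no result, because the exposure comes from the absent grade term.
- **Grade may be part of what is sought.** The objective is a same-stage comparison, not one at equal aggressiveness, and the hypothesis links the African-American profile to faster progression. If race acts through grade, adjustment removes some of the signal. The unadjusted contrast is therefore legitimate. This argues for reporting both contrasts, not for replacing one.
- **Thin evidence on imbalance.** The Introduction's statement concerns autopsy findings across populations, not Gleason within pT strata of prostatectomy patients in Baltimore. Part of that gradient may be tumor size, which staging partly captures. Direction and size are unknown.
- **Exploratory setting.** Genes are selected by FDR, not at a fixed 0.05, and candidate markers of progression and outcome go on to quantitative PCR. PCR can confirm that expression differs, but it cannot say whether race or grade is the reason.
- **Possible analysis-plan detail.** Covariates are often left to a separate plan. Here, however, 5.4.3 itself fixes the groups and contrasts, and the comment is on what it fixes.

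**Conclusion.** The point holds as a gap in interpretation. The stated analysis compares races within pT stage only, and it could not distinguish a race signature from a difference in Gleason mix.

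A reader might go further and infer that the race gene list will be a grade artifact. The documents do not support that: they give no Gleason distribution by race, and with equal mixes there is no inflation.

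The rates in the working rest on assumed shares, an assumed 1 log2 grade effect and an assumed within-grade SD. They apply per gene and only to grade-responsive genes. At 0.001 they run from about 5 to about 140 times nominal (0.5%/0.1% to 14%/0.1%).

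A separate, minor point is that the 24.5% is a stage-only figure and so only a lower bound for the stage-or-Gleason expectation it is placed beside.

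**What to change.** 1. In 5.4.3 keep the race-by-pT contrasts and add a version adjusted for Gleason group (6 or lower versus 7 or higher, the split already defined for the genotype analysis). Report it beside the unadjusted contrast.
2. Tabulate Gleason group by Table 6 cell.
3. In 1.2.4 label 24.5% (12/49) as pathological stage alone. If the stage-or-Gleason share is wanted for planning, give it separately.

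The cost is one error degree of freedom in the adjusted model. The adjusted contrast may be attenuated if race acts through grade, which is why both are reported. Where a Table 6 cell contains almost only one Gleason group, the adjustment will carry little information, and the tabulation will show this.
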